Setting: The study will be conducted in KMP. The community is a resource-limited, densely populated, high HIV/TB disease burden area in Cape Town. The DTHF Tutu Tester Mobile Clinics offer mobile HIV testing days in various locations in KMP. Specifically, there are four high HIV disease burden communities in the district; Philippi (population n=200,803), Crossroads (n=36,043), Gugulethu (n=98,468) and Nyanga (n=57,996). In addition to our well-established relationship with community organisations such as an independent advisory board, we have provided HIV testing services and linkage to treatment from the mobile clinic since 2008 and are currently partnering with the KMP subdistrict health team in providing COVID screening and testing. Given our long-term relationship with and service in the community, our relationships with the Provincial Department of Health, and our experience with the research platforms, it is feasible for us to successfully execute the proposed

research. The mobile clinic team will provide a screening service and SARS-CoV-2 polymerase chain reaction (PCR) testing with the GeneXpert or courier samples to accredited laboratories and rapid testing with the SARS-CoV-2 antibody COVID-19 IgG/IgM Rapid Test Device. Additionally, the mobile clinic team will offer screening for HIV, TB, STI and chronic diseases (e.g. diabetes, hypertension, and obesity).

Design: A cluster randomised controlled study with longitudinal follow up of SARS-CoV-2 infection in 120 households which have newly diagnosed SARS-CoV-2 positive cases. The index cases and their household contacts will be invited to participate in the study after informed consent. Baseline surveys and screening and then weekly screening of HHC will occur (Table 1). These household contacts will be tested at 0, 1, 2, 3 and 4 weeks.

The study design is a type 2 hybrid cluster (household) randomised controlled trial, with outcomes assessed on index patients and their household contacts (Diag 1). 120 consecutively newly diagnosed index patients (GeneXpert SARS-CoV-2 PCR) and up to 8 household contacts will be invited to participate in the trial as part of the prospective observational study evaluating transmission and symptoms. After completing consent, households will be randomised in a 1:1 ratio in blocks of 10 (60 households per group; 360 patient and household contacts per group).

Diagram 1: Study flow

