Control group households will receive standard Western Cape Department of Health COVID-19 recommendations for transmission mitigation at the time of diagnosis. Currently this includes advice on physical distancing, hand and respiratory hygiene and cleaning. Information has been distributed through dissemination of written pamphlets, WhatsApp messages, telephone hotlines and websites. Home care is only recommended if there is a separate room. Facility isolation and quarantine services are available for households without separate rooms, and are strongly advised should members of the household be considered at risk for severe COVID-19 (age ≥ 55 years and/or underlying chronic conditions especially diabetes). But uptake of such services has been lower than expected and beds are being decommissioned. Intervention group households will receive intensive support delivered by CHWs (See Table 1). This will comprise an initial household assessment to assess needs for facility isolation or quarantine referral, explain infection control measures and help the household adapt

them to their homes, provision of basic supplies (masks, hand sanitiser and bleach) and written materials at appropriate literacy levels and in local language. The same CHWs will follow-up household members daily for the first two weeks and three times a week during weeks 2-4, as well as distribute pre-prepared twice daily text messages. Two CHWs will be assigned per household to sustain intensive support and prevent burnout.

Table 1: Interventions

Characteristic	Usual care (outside study)	Enhanced Usual Care	StopCov intervention
Testing of household contacts	Not routinely available. Limited to symptomatic individuals at risk of severe COVID-19.*	At baseline and weekly for up to 8 household contacts ≥ 12 years.	At baseline and weekly for up to 8 household contacts ≥ 12 years.
Facility based isolation and quarantine	Available but uptake limited.	Available but uptake limited.	Counselled to take up service if isolation at home not possible and person in household at risk for severe COVID-19.
Hospital care	Available through clinical services/ hotline	Available through clinical services/ hotline	Available through clinical services/ hotline

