Written material	Extensive content available online. Limited content available as pamphlets and WhatsApps. No systematic distribution of WhatsApp messaging.	Printed copies of PACK Home Volume 1 (Be coronavirus safe) and Volume 2 (COVID-19 Caring at home).	Printed copies of PACK Home Volume 1 and 2. WhatsApp optimised versions of content delivered daily.
Community Health Worker visits	Mainly alongside chronic medication delivery.	Mainly alongside chronic medication delivery.	Additional one off household assessment to establish relationship at baseline.
Equipment	Distributed through drives.	Masks and hand sanitiser at enrolment.	Masks, hand sanitiser, bleach, gloves (to wear when using bleach). Plus on demand during follow-up.
Telephonic and text message support	On demand hotline service.	On demand hotline service	Scheduled support: Active phase (until 14 days after last person in household diagnosed): daily.

			Follow-up phase: 3 times a week for 7-14 days. Close-out: 5 days (to facilitate full integration into usual services).
--	--	--	---

* As of 06/07/2020 patients are considered at risk of severe COVID-19 if they are: 55 years or older or of any age with any one of the following: diabetes, on TB treatment, HIV, kidney disease, hypertension, previous TB, chronic lung disease, on cancer treatment.

Outcomes will be independently assessed by research staff who are also collecting biological samples at 0, 1, 2, 3, and 4 weeks. Baseline surveys will collect information on demographics, COVID-19 symptoms, household tracing information and home/ dwelling characteristics that impact transmission (size, rooms, ventilation, access to safe water, laundry facilities). Patient and household contact surveys will also include standardised measures to assess psychosocial functioning: General Health Questionnaire; UCLA Loneliness Scale and a version of the Brief AIDS-Related Stigma scale adapted for COVID-19. Research staff will complete a checklist documenting uptake of infection control measures at all follow-up contacts (1, 2, 3, 4 weeks). A sample size of 120 households (60 per group; 320 patient and household contacts per group) will provide 80-99% power to detect a 40% reduction in R₀ (2.5 to 1.5) varying the intra-cluster correlation efficient from 0.90 (80%) to 0.05 (99%) (Table 3). Index patients and their contacts will be reimbursed with R150 for their time at the baseline and final study visits.

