Overview

A cluster randomised controlled study with longitudinal follow up of SARS-CoV-2 infection in 120 households which have newly diagnosed positive cases. The index cases and their HHC will be invited and enrolled after informed consent. Baseline surveys and SARs-CoV-2 screening (PCR and IgM/IgG serology) and then weekly SARs-CoV-2 screening (PCR and serology) of HHC will occur at 0, 1, 2, 3 and 4 weeks. The households will be randomized to an intensified COVID19 infection mitigation intervention (n=60) administered by CHWs vs the standard messaging (n=60). Please see Figure 1 for a schematic overview of the study design.

EUC = enhanced usual care

Figure 1: Flow chart and schematic overview of the study design.

Sample Size Determination

We calculated the different effect sizes (Table 1). Based on exponential test for comparing hazards, assuming $120*6=720$ subjects, different intraclass correlation coefficients (ICCs) and comparing $R_0=2.5$ (with resulting incidence of 0.208 among 720 subjects) to a reduced R_0 of 0.9 (64% reduction, with resulting incidence of 0.075 among 720 subjects) or 1.25 (50% reduction) or 1.5 (40% reduction).

Table 1: ICC calculations

ICC	R0 2.5 to 0.9	R0 2.5 to 1.25	R0 2.5 to 1.5
	64% reduction	50% reduction	40% reduction
0.05	1.00000	1.00000	0.999944
0.25	1.00000	0.999891	0.991312
0.50	0.999993	0.995042	0.935880
0.75	0.999729	0.972942	0.846222
0.90	0.999033	0.951485	0.792745

Randomization and stratification

After completing consent, households will be randomised in a 1:1 ratio in blocks of 10 (60 households per group; 360 patient and household contacts per group).

Overview of data and data sources for analysis

All data are collected with two individual identifiers: study ID and PID (Western Cape Government health number). The exception is data source #4, which only uses PID.

1. Redcap database
 - a. Baseline survey of index patient and household characteristics (demographics, COVID-19 symptoms, household tracing information, home/dwelling characteristics that impact transmission (size, rooms, ventilation, access to safe water, laundry facilities))
 - b. Uptake of infection control measures at all follow-up contacts (assessment of use of isolation measures and cleaning of household surfaces up to 10 days post case of last diagnosis in household, at 1, 2, 3, 4 weeks).

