 - c. Assessment data of psychosocial functioning (General Health Questionnaire 9 for mood; UCLA Loneliness Scale and a version of the Brief AIDS-Related Stigma scale adapted for COVID-19, at baseline and at week 4);
 - d. Results of serology (pos/neg, no titres) and nasopharyngeal swabs for PCR of HHCs at baseline, and at weeks 1, 2, 3 and 4);
2. Randomisation list
3. Qualitative and quantitative process data on intervention (STOPCOV database)
 - a. Number and duration of calls to households
 - b. transcripts from follow-up calls
 - c. SMS/WhatsApp data
 - d. transcripts from interviews with STOPCov counsellors and intervention/control index and HHC participants
4. Provincial health data(PID; all study participants and household contacts)

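### One disclosed block size of 10, with no concealment procedure described, lets anyone tracking allocations deduce up to 1 in 6 household assignments; larger masked blocks with concealed release are a cheap improvement

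*Protocol*

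**What the plan says.** The allocation rule appears three times in the same words: in the Protocol's TRaCE Schema (Design), in the Protocol's Approach (Design), and in SAP section 3. It reads: "After completing consent, households will be randomised in a 1:1 ratio in blocks of 10", giving "60 households per group; 360 patient and household contacts per group". The SAP places it under the heading "Randomization and stratification", but no stratification factor follows. SAP section 3 also names a "Randomisation list", in the singular, as data source 2. Neither document says who generates, holds or releases that list, or how the next assignment is kept from recruiting staff.

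The arms differ in ways that field staff can see. In the Protocol's account of the intervention group, "Two CHWs will be assigned per household to sustain intensive support and prevent burnout". In Table 1 the equipment for STOPCOV households is "Masks, hand sanitiser, bleach, gloves (to wear when using bleach). Plus on demand during follow-up", while enhanced usual care households get masks and sanitiser once, at enrolment. The documents do not use the term open-label; it is inferred from these differences.

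On the order of events, the Approach (Design) puts randomisation after consent. The Process row of the Schema has the household randomised after enrolment and then, in the following sentence, each occupant invited, with consent procedures after that.

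**The concern.** With one known block size and a 5:5 split, the end of each block gives itself away. Once one arm has received its five households, every remaining assignment in that block is fixed. Staff who can see which households received STOPCOV could work this out by counting.

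The comparison at stake is the Aim 2 primary endpoint (SAP 7.2). It is free of selection bias only if the households and contacts entering each arm do not depend on the coming assignment. A recruiter who knows the next arm could vary the timing of an approach, or the effort put into enrolling up to eight contacts. A difference in risk created in this way would look like an effect of STOPCOV.

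**Working it through.** **Inputs.** Block size 10, so m = 5 per arm per block (Protocol, Approach, Design; SAP section 3). 120 households, 60 per arm (same places). Recruitment over 1 to 3 months (Protocol, Schema, Duration).

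**The plan's own figure.** 120 / 10 = 12 complete blocks, and 12 × 5 = 60 per arm. This matches. The documents give no predictability figure to reproduce.

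**Assignments that can be deduced.** In a block of 2m, the expected number of assignments made after one arm is used up is 2m/(m + 1).
- 2 × 5 / (5 + 1) = 1.667 per block, or 1.667/10 = 16.7% (1 in 6).
- Over 12 blocks: 12 × 1.667 = 20 of 120 households.
- Enumerating all 252 orderings of a 5 + 5 block gives the same mean. Every block has at least one such position: exactly one in 55.6% of blocks, two in 27.8%, three or more in 16.7%.

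**Best-guess rate.** Always guessing the arm with more places left in the block gives m + (4^m / C(2m, m) − 1)/2 correct guesses per block.
- 5 + (1024/252 − 1)/2 = 6.53 of 10, or 65.3%, against 50% with no information.
- About 24% of assignments can be guessed with probability 75% or more. That share includes the 16.7% that are certain.

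**Range.** These figures assume an observer who knows the block size, where each block starts and every earlier assignment. If the earlier assignments or the block boundaries are unknown, the number deducible with certainty is 0. The range is therefore 0 to 16.7%.

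**Alternatives**, simulated against an observer who knows the set of sizes and every earlier assignment:

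| Block sizes | Certain | Best guess correct |
|---|---|---|
| Fixed 10 | 16.7% | 65.3% |
| 4, 6, 8 | 2.2% | 67.9% |
| 6, 8, 10 | 1.6% | 66.3% |
| 8, 10, 12 | 1.4% | 65.0% |
| 12, 16, 20, 24 | 0.6% | 61.7% |

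For the last row, the share guessable at 75% or more falls from about 24% to 9.7%. The final split differs from equality by 1.2 households on average (maximum 8 in simulation). Small mixed blocks remove certainty but leave the overall guess rate no better, or slightly worse, so larger sizes are the useful choice.

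**Possible bias (assumption, for scale only).** Suppose all 20 certain households, 10 per arm, are steered so that contact risk is 25% below average in STOPCOV and 25% above in usual care. With no true effect the risk ratio is (50 + 10 × 0.75)/(50 + 10 × 1.25) = 57.5/62.5 = 0.92. If half of them are steered, it is (55 + 5 × 0.75)/(55 + 5 × 1.25) = 58.75/61.25 = 0.96. With no steering it is 1.00.

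**The case against.** Several stronger readings are tempting, and the documents do not support them.

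- **That 1 in 6 assignments are actually known before enrolment.** This is an upper bound. Cases come from two sources, the mobile units and public-sector clinics, so one recruiter may not see every earlier assignment. Nothing shows that recruiters know the block boundaries.
- **That a single team recruits, randomises and delivers.** The documents do not say so. The investigator list includes a statistics department and other institutions, and the list may already be held centrally. The documents supplied do not settle this.
- **That no planned analysis could reveal the problem.** SAP 6.1 reports numbers screened and enrolled and the time from the index case's positive test to enrolment. SAP 6.3 summarises baseline characteristics. The SAP 7.1 models, to which 7.2 adds study arm, allow for confounders and baseline values. These can show or partly adjust for measured differences, but not unmeasured ones.
- **That steering is likely or large.** Invitation is consecutive and randomisation follows consent. At the planned pace a block fills in about 2.5 to 7.5 days (30/12 to 90/12), which leaves little room to delay a household. The 0.92 illustration requires every certain household to be steered in the harmful direction, and even then the spurious 8% reduction is far below the 40% to 64% reductions used in the power table.

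Two further points stand. A fixed block of 10 is already less predictable than a fixed block of 4, 6 or 8 (33%, 25% and 20% certain), so the weakness is a single disclosed size without concealment text, not the number 10. Masked blocks lower the guess rate only from about 65% to 62%, so they supplement concealed release and cannot replace it.

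The objection does not remove the point. Consecutive invitation does not govern how contacts are persuaded to join, and consent before randomisation does not protect an assignment that can be deduced before consent.

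**Conclusion.** The point holds as a cheap improvement to a stated method. It is not evidence that allocation was subverted. Up to 16.7% of assignments (at most about 20 of 120) could be deduced, and about 65% guessed correctly, by someone tracking allocations with full knowledge of the blocks; the lower limit for deducible assignments is 0. The conclusion rests on two inferences: that the arms are visible to field staff, and that the absence of any strata or concealment step in the text means none is specified.

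The order of events in the Process row of the Schema may matter more than the blocks. If occupants are invited after the household's arm is known, contact enrolment could differ by arm in all 120 households without anyone predicting anything, and no choice of block size would close that route. The row can also be read as consistent with consent first, since it opens by inviting index cases and their households to enrol. It needs clarifying either way.

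**What to change.** 1. **For households still to be randomised**, replace the blocks-of-10 wording in both Protocol Design passages and in SAP section 3 with: permuted blocks of randomly varying size, generated by the trial statistician, with the sizes kept in a restricted document and withheld from recruiting staff and CHWs. Sizes such as 12, 16, 20 and 24 would serve, and the actual set should not be printed in the Protocol or SAP.
2. **State the concealment procedure**: who holds the list, and that each assignment is released singly, only after the index case and contacts have consented and been enrolled. If such a procedure is already in use, write it down.
3. **Reconcile the Process row of the Schema with the Approach (Design)**, so that contacts are enrolled before the arm is known.
4. **For households already randomised in blocks of 10**, add a sensitivity analysis of SAP 7.2 that leaves out households in deducible positions (one arm already at five within the block). Compare their baseline household risk and number of contacts enrolled with those of the rest. At most about 20 households are expected in this group, so the comparison has limited power and a null result would not be reassuring on its own.

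Item 4 may carry most of the value. The Protocol plans the study for June 2020 to January 2021, and the SAP cites a Protocol dated 15 December 2020, so much of the list may already be used.

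The cost is a regenerated list for the remaining households, a few sentences, and a minor extra analysis from the ordered randomisation list, which is already an SAP data source. The downside is a small possible departure from 60:60, about 1 household on average, with negligible loss of power.

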8.3. The proportion of index patients and HHC that showed improved psychosocial functioning in the intervention arm as compared to the enhanced usual care (EUC) arm. 10	
8.4. The association between the time to transmission and clinical symptoms of the index cases.....	10
8.5. The symptomatic/asymptomatic ratio among transmitted SARS-CoV-2 in household contacts	10
8.6. The incidence of SARS-CoV-2 transmitted to HHC of the index COVID19 cases over a 4 week period, stratified by COVID-19 wave.....	10
8.7. Analysis of household exposure to SARS-CoV-2 at baseline using the baseline serology result, and development of antibodies using the serology result during follow-up. 10	
8.8. Process Evaluation Analysis.....	11

1. ***INTRODUCTION***

This Statistical Analysis Plan (SAP) describes the statistical methods to be used during the analysis and reporting of data collected for the TRACE study. This SAP should be read in conjunction with the Study Protocol (dated 15 December 2020), Case Report Forms (CRFs, Final Versions, dated 4 November 2020) and Data Management Plan (DMP, dated 18 June 2020).

2. ***OBJECTIVES OF THE STUDY***

2.1. **Primary objectives**

1. To measure frequency and timing of transmission of SARS-CoV-2 to household contacts.
2. To investigate the effect of an intensive infection mitigation intervention (STOPCOV) administered by lay health care workers on the household transmission of SARS-CoV-2.

[figure not shown]
2.2. **Secondary objectives**

1. To investigate the effect of the STOPCOV intervention on clinical outcomes and psychosocial functioning
2. To investigate the difference in transmission of SARS-CoV-2 to HHC stratified by COVID-19 wave (first or second wave)
3. To describe the household exposure to SARS-CoV-2 at baseline using the baseline serology result, and development of antibodies using the serology result during follow-up.
4. To assess acceptability, feasibility and contextual factors impacting intervention delivery (process evaluation), specifically:
 - a. To understand the acceptability and feasibility of the STOPCov intervention.
 - b. To understand how context shapes implementation of the STOPCov intervention at the level of households and individuals.
 - c. To provide explanations for observed trends in the trial findings.
 - d. To generate theoretical generalisations of how to optimise wider implementation of the STOPCov intervention to other households to reduce transmission of COVID-19.

3. ***DESIGN OF THE STUDY***

Overview

A cluster randomised controlled study with longitudinal follow up of SARS-CoV-2 infection in 120 households which have newly diagnosed positive cases. The index cases and their HHC will be invited and enrolled after informed consent. Baseline surveys and SARs-CoV-2 screening (PCR and IgM/IgG serology) and then weekly SARs-CoV-2 screening (PCR and serology) of HHC will occur at 0, 1, 2, 3 and 4 weeks. The households will be randomized to an intensified COVID19 infection mitigation intervention (n=60) administered by CHWs vs the standard messaging (n=60). Please see Figure 1 for a schematic overview of the study design.

EUC = enhanced usual care

Figure 1: Flow chart and schematic overview of the study design.

Sample Size Determination

We calculated the different effect sizes (Table 1). Based on exponential test for comparing hazards, assuming $120*6=720$ subjects, different intraclass correlation coefficients (ICCs) and comparing $R_0=2.5$ (with resulting incidence of 0.208 among 720 subjects) to a reduced R_0 of 0.9 (64% reduction, with resulting incidence of 0.075 among 720 subjects) or 1.25 (50% reduction) or 1.5 (40% reduction).

Table 1: ICC calculations

ICC	R0 2.5 to 0.9	R0 2.5 to 1.25	R0 2.5 to 1.5
	64% reduction	50% reduction	40% reduction
0.05	1.00000	1.00000	0.999944
0.25	1.00000	0.999891	0.991312
0.50	0.999993	0.995042	0.935880
0.75	0.999729	0.972942	0.846222
0.90	0.999033	0.951485	0.792745

Randomization and stratification

After completing consent, households will be randomised in a 1:1 ratio in blocks of 10 (60 households per group; 360 patient and household contacts per group).

Overview of data and data sources for analysis

All data are collected with two individual identifiers: study ID and PID (Western Cape Government health number). The exception is data source #4, which only uses PID.

1. Redcap database
 - a. Baseline survey of index patient and household characteristics (demographics, COVID-19 symptoms, household tracing information, home/dwelling characteristics that impact transmission (size, rooms, ventilation, access to safe water, laundry facilities))
 - b. Uptake of infection control measures at all follow-up contacts (assessment of use of isolation measures and cleaning of household surfaces up to 10 days post case of last diagnosis in household, at 1, 2, 3, 4 weeks).
 - c. Assessment data of psychosocial functioning (General Health Questionnaire 9 for mood; UCLA Loneliness Scale and a version of the Brief AIDS-Related Stigma scale adapted for COVID-19, at baseline and at week 4);
 - d. Results of serology (pos/neg, no titres) and nasopharyngeal swabs for PCR of HHCs at baseline, and at weeks 1, 2, 3 and 4);
2. Randomisation list
3. Qualitative and quantitative process data on intervention (STOPCOV database)
 - a. Number and duration of calls to households
 - b. transcripts from follow-up calls
 - c. SMS/WhatsApp data
 - d. transcripts from interviews with STOPCov counsellors and intervention/control index and HHC participants
4. Provincial health data(PID; all study participants and household contacts)

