Household Contacts (HHC)						
	ICF		x			
	Demography survey		x			
	Symptom check	x		x	x	x
	COVID19 PCR	x		x	x	x
	COVID serology	x		x	x	x
	Follow up surveys	x		x		x

Data Collection and Management: Data will be collected by study staff on handheld devices. Data will be downloaded daily to a central database housed at the DTHF head office. Further details are available in Work Package 5 and the Data Management document.

Statistical Analysis and sample size: We will describe and compare the characteristics and survey outcomes, isolation, and linkages of participants. We calculated the different effect sizes (Table 2). Based on exponential test for comparing hazards, assuming $120*6=720$ subjects, different intraclass correlation coefficients (ICCs) and comparing $R_0=2.5$ (with resulting incidence of 0.208 among 720 subjects) to a reduced R_0 of 0.9 (64% reduction, with resulting incidence of 0.075 among 720 subjects) or 1.25 (50% reduction) or 1.5 (40% reduction).

Table 3: ICC calculations

ICC	Ro 2.5 to 0.9	Ro 2.5 to 1.25	Ro 2.5 to 1.5
	64% reduction	50% reduction	40% reduction
0.05	1.00000	1.00000	0.999944
0.25	1.00000	0.999891	0.991312
0.50	0.999993	0.995042	0.935880
0.75	0.999729	0.972942	0.846222
0.90	0.999033	0.951485	0.792745

The analyses will be determined by the study analysis plan. These analyses include the calculation of the proportion of SARS-CoV-2 positive individuals screened over a 3-month period, the transmissibility of the virus by determining the proportion of SARS-CoV-2 transmitted to household contacts of the identified COVID19 cases over a 4-week period, the period of infectiousness by correlating the time to transmission and clinical symptoms of the index cases, and the symptomatic/asymptomatic ratio among transmitted SARS-CoV-2 in household contacts. The Ro will be determined by both looking at new cases among the population in contact with the index cases and the total population (both in our service and other clinics in the area) diagnosed over time. The main outcome relates to the incidence of new cases of COVID19. These will be analysed using mixed effect Poisson regression models and frailty models to take the clustering by household into account. Both these regression models take the duration of follow up into account. Scores (e.g., GHQ) will be baseline adjusted. Qualitative data will be transcribed, translated and inductively analysed for themes.

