7. ANALYSIS OF PRIMARY STUDY OUTCOMES

7.1. The proportion of SARS-CoV-2 transmitted to HHC of the index COVID19 cases over a 4 week period

SARS-CoV-2 infection in a HHC will be defined as a positive PCR or evolving positive serologic test in a HHC who had a negative PCR or negative serology at baseline. The incidence of SARS-CoV-2 infection in HHC will be calculated as the number of new cases divided by the person time at risk and 95% confidence intervals calculated based on the Poisson distribution adjusted for clustering by household. This incidence as well as the timing to transmission will be analysed using exponential shared frailty models taking the clustering by household into account and allowing for censoring. The start time will be the date of diagnosis of the index case and the event time the date of diagnosis of the HHC using the date of the first positive test based on PCR or serology. Models will include possible confounders including adjustment for baseline values.

7.2. The proportion of transmissions to HHC in the enrolled households of index COVID cases assigned to the infection mitigation intervention arm compared with the households in the enhanced usual care (EUC) arm.

The incidence of SARS-CoV-2 will be estimated for the different study arms and incidence of and timing to SARS-CoV-2 per study arm will be compared by including study arm in the exponential frailty models.

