8.5. The symptomatic/asymptomatic ratio among transmitted SARS-CoV-2 in household contacts

The proportion of symptomatic and asymptomatic transmitted SARS-CoV-2 infections will be calculated, overall, with 95% confidence intervals based on binomial or asymptotic normal distributions.

8.6. The incidence of SARS-CoV-2 transmitted to HHC of the index COVID19 cases over a 4 week period, stratified by COVID-19 wave.

The incidence of SARS-CoV-2 will be compared by COVID-19 wave using exponential frailty models and including an indicator of the wave in the model.

The COVID19 wave will be defined as follows:

- wave 1: date of diagnosis of index case between 1 May and 31 November
- wave 2: date of diagnosis of index case from 1 December onwards

8.7. Analysis of household exposure to SARS-CoV-2 at baseline using the baseline serology result, and development of antibodies using the serology result during follow-up.

Longitudinal weekly prevalence profiles of serology results will be summarized overall and by study arm. These profiles can be analysed using hierarchical mixed effect logistic regression models with both household and HHC as nested random effects. Time to development of antibodies can be analysed using exponential frailty models. Models will include baseline serology results.

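### SAP 8.6 compares transmission between COVID-19 waves without committing to account for contacts' baseline antibodies, so the wave rate ratio can mix a change in susceptible contacts with a change in transmission

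*SAP*

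**What the plan says.** - **Objective.** SAP 2.2, objective 2: "To investigate the difference in transmission of SARS-CoV-2 to HHC stratified by COVID-19 wave (first or second wave".
- **Wave analysis.** SAP 8.6: "The incidence of SARS-CoV-2 will be compared by COVID-19 wave using exponential frailty models and including an indicator of the wave in the model". No restriction on contacts and no other covariate is named.
- **Waves.** Also in 8.6, households are split by calendar date of the index diagnosis, with "wave 2: date of diagnosis of index case from 1 December onwards". The printed end date of wave 1 does not exist and no year is given. That is a wording slip and does not affect this point.
- **Risk set.** SAP 7.1 counts as a new infection a positive PCR or evolving serology "in a HHC who had a negative PCR or negative serology at baseline". The event date is that of the first positive PCR or serology. 7.1 also promises adjustment for possible confounders and baseline values, without naming any.
- **Baseline serology as a model term.** Only SAP 8.7 names it, for the antibody-profile and time-to-antibody models: "Models will include baseline serology results".
- **Data.** SAP section 3 lists baseline PCR and serology for contacts, with serology as positive or negative and no titres. The contact eligibility criteria in the Protocol do not exclude earlier infection or existing antibodies.

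**The concern.** The 'or' in 7.1 keeps a PCR-negative, antibody-positive contact in the denominator. With a positive/negative result only, that contact cannot newly turn positive on serology, so one of the two routes to an event is essentially closed. This lowers the measured event risk by definition, and lowers it further if earlier infection protects.

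Randomisation balances such contacts between arms in expectation. It does nothing to balance them between waves. Wave 2 households were enrolled after the period that the SAP calls wave 1, so a different antibody-positive share is plausible. If the shares differ, the wave coefficient in 8.6 reflects both who could still be infected and how readily the virus spread. The report could then show a change between waves when transmission was the same, or hide a real one.

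**Working it through.** The documents give no figure for the wave comparison, no seroprevalence and no expected split of households by wave. The power table concerns the arms. There is therefore no plan figure to reproduce, and the shares and risk reductions below are assumptions.

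**Step 1: simple risk ratio.** Let s1 and s2 be the antibody-positive shares in waves 1 and 2, and k the relative reduction in measured event risk in those contacts. With equal true transmission to antibody-negative contacts:

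apparent ratio = (1 − s2·k) / (1 − s1·k)

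| k | s1 = 5%, s2 = 40% | s1 = 15%, s2 = 20% |
|---|---|---|
| 1.0 | 0.60/0.95 = 0.63 | 0.80/0.85 = 0.94 |
| 0.8 | 0.68/0.96 = 0.71 | 0.84/0.88 = 0.95 |
| 0.5 | 0.80/0.975 = 0.82 | 0.90/0.925 = 0.97 |

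The range is 0.63 to 0.97. Read the other way, a true wave 2 rise by a factor of 1.03 (0.925/0.90) to 1.58 (0.95/0.60) would appear as no change.

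**Step 2: person-time check.** SAP 7.1 uses events over person-time. Take p = 0.208, the incidence in the SAP's sample size section, as the four-week risk in antibody-negative contacts. The weekly hazard is then λ = −ln(1 − 0.208)/4 = 0.0583, and mean time at risk is 0.208/0.0583 = 3.57 weeks. Antibody-positive contacts have hazard r·λ.

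Worked case, shares 10% and 30%, r = 0:
- Wave 1: (0.90 × 0.208)/(0.90 × 3.57 + 0.10 × 4) = 0.0518 per week
- Wave 2: (0.70 × 0.208)/(0.70 × 3.57 + 0.30 × 4) = 0.0394 per week
- Ratio: 0.76

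| Shares, wave 1 / wave 2 | r = 0 | r = 0.2 | r = 0.5 |
|---|---|---|---|
| 5% / 20% | 0.83 | 0.87 | 0.92 |
| 10% / 30% | 0.76 | 0.82 | 0.89 |
| 20% / 50% | 0.60 | 0.70 | 0.83 |

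With p = 0.417 (60 × 2.5/360, using one arm as denominator) the 10%/30% row becomes 0.74, 0.80 and 0.89, so the result is not sensitive to p.

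**Step 3: where the effect vanishes or turns.**
- Equal shares, or r = 1: ratio 1.00.
- Shares reversed (30%/20%), r = 0: ratio 1.16.
- A positive baseline serology in a PCR-negative contact counted as the first positive test (assumed at half a week), shares 10%/30%: (0.1456 + 0.30)/(0.70 × 3.57 + 0.15) over (0.1872 + 0.10)/(0.90 × 3.57 + 0.05) = 0.168/0.088 = 1.91. The same data point the other way.

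**Step 4: false positive wave differences.** Assume 360 contacts per wave, shares 10%/30%, r = 0.2, and a design effect of 1 + 5·ICC for six per household. A nominal 5% test of the log rate ratio then rejects in 18% (ICC 0.05) or 12% (ICC 0.25) of trials at p = 0.208, and in 35% or 22% at p = 0.417, although transmission is equal.

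**Step 5: after the change.** Restricting to contacts negative on both tests, or stratifying by serostatus, gives 1.00 in every equal-transmission scenario.

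**The case against.** **Serostatus may already be covered.** 8.6 can be read as adding a wave term to the 7.1 model, and 7.1 promises baseline adjustment. This stands in part: the plan does not rule out adjusting for serology. It does not commit to it either. 8.6 does not repeat the sentence, and 8.7 shows that serology is named where it is meant.

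**A reader might infer that wave 2 will look like a wave with less transmission.** The documents do not support that. They give no seroprevalence and no protection figure, and step 3 shows that the direction depends on the shares and on how 7.1 is read. The Protocol plans recruitment over one to three months. If that window straddled 1 December, wave 1 households would have been enrolled late in wave 1 and the shares could be close.

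**A reader might extend the point to the household R0.** The Protocol says "The Ro will be determined by both looking at new cases among the population in contact with the index cases", but no analysis of R0 by wave is planned. The R0 comparison that it describes is between randomised arms, where serostatus is balanced in expectation.

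**Antibody-positive contacts are not always past cases.** Time at risk starts at the index diagnosis, and a contact may have been infected in the current household episode. If IgM and IgG are recorded separately, a contact could also still evolve on serology. Both stand. They make serostatus an imperfect marker and argue against showing only the restricted comparison.

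**Incidence among contacts as found is a legitimate target.** True, and it should be kept. But the objective is worded as a difference in transmission, which that figure alone does not isolate.

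**Conclusion.** The point holds as a conditional one. As written, the wave comparison does not commit to separating contacts by baseline antibody status, and the 7.1 risk set leaves PCR-negative, antibody-positive contacts in. If their share differs by wave, the reported ratio is displaced: to about 0.63–0.97 under the shares and risk reductions assumed in step 1, to no extent with equal shares, and above 1 under the alternatives in step 3. All of these sizes rest on assumed inputs; the wording of 7.1 and 8.6 does not.

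The reach is limited to one secondary, non-randomised comparison. The randomised arm comparison is not called into question by it. The change is still worth making, because it is nearly free and could alter what is concluded about the waves.

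**What to change.** - **SAP 7.1:** state whether being at risk requires both baseline tests to be negative ('and' in place of 'or'), and that a positive baseline test is not a new event.
- **SAP 8.6:** name baseline serostatus as a covariate or stratum in the wave model. Report the comparison among contacts negative on both baseline tests alongside the all-contact comparison.

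The cost is SAP wording and one extra model. The baseline tests are already collected, and SAP section 5 places sign-off before database lock. The restricted comparison has fewer contacts: with 360 per wave assumed, 720 falls to 630 at shares of 5%/20% (342 + 288) or 576 at 10%/30% (324 + 252). It may also drop some contacts infected early in the current household episode, which is why both comparisons should be shown.
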